11.0 STUDY-SPECIFIC COMMITTEES

Study specific committees are detailed in Section 3.3.

12.0 DATA HANDLING AND RECORDKEEPING

The full details of procedures for data handling will be documented in the Data Management Plan. If selected for coding, AEs, pretreatment events, medical history, and concurrent conditions will be coded using the Medical Dictionary for Regulatory Activities (MedDRA). Drugs will be coded using the World Health Organization Drug Dictionary.

12.1 eCRFs

Completed eCRFs are required for each subject who signs an ICF.

The sponsor or its designee will supply investigative sites with access to eCRFs and arrange to train appropriate site staff in the use of the eCRF. These forms are used to transmit the information collected in the performance of this study to the sponsor, CRO partners, and regulatory authorities. Investigative sites must complete eCRFs in English.

After completion of the entry process, computer logic checks will be run to identify items, such as inconsistent dates, missing data, and questionable values. Queries may be issued by Takeda personnel (or designees) and will be answered by the site.

Any change of, modification of, or addition to the data on the eCRFs should be made by the investigator or appropriate site personnel. Corrections to eCRFs are recorded in an audit trail that captures the old information, the new information, identification of the person making the correction, the date the correction was made, and the reason for change.

The principal investigator must review the eCRFs for completeness and accuracy and must sign and date the appropriate eCRFs as indicated. Furthermore, the principal investigator must retain full responsibility for the accuracy and authenticity of all data entered on the eCRFs. ePROs and therefore PRO data are not included in the eCRF and should not be reviewed by the principal investigator.

eCRFs will be reviewed for completeness and acceptability at the study site during periodic visits by study monitors. The sponsor or its designee will be permitted to review the subject's medical and hospital records pertinent to the study to ensure accuracy of the eCRFs. The completed eCRFs are the sole property of the sponsor and should not be made available in any form to third parties, except for authorized representatives of appropriate governmental health or regulatory authorities, without written permission of the sponsor.

12.2 Record Retention

The investigator agrees to keep the records stipulated in Section 12.1 and those documents that include (but are not limited to) the study-specific documents, the identification log of all participating subjects, medical records, temporary media such as thermal sensitive paper, source worksheets, all original signed and dated ICFs, subject authorization forms regarding the use of personal health information (if separate from the ICFs), electronic copy of eCRFs, including the audit trail, and detailed records of drug disposition to enable evaluations or audits from regulatory authorities, the sponsor or its designees. Any source documentation printed on degradable thermal sensitive paper should be photocopied by the site and filed with the original in the subject's chart to ensure long term legibility. Furthermore, ICH E6 Section 4.9.5 requires the investigator to retain essential documents specified in ICH E6 (Section 8) until at least 2 years after the last approval of a marketing application for a specified drug indication being investigated or, if an application is not approved, until at least 2 years after the investigation is discontinued and regulatory authorities are notified. In addition, ICH E6 Section 4.9.5 states that the study records should be retained until an amount of time specified by applicable regulatory requirements or for a time specified in the Clinical Study Site Agreement between the investigator and sponsor.

Refer to the Clinical Study Site Agreement for the sponsor's requirements on record retention. The investigator should contact and receive written approval from the sponsor before disposing of any such documents.

13.0 STATISTICAL METHODS

13.1 Statistical and Analytical Plans

A statistical analysis plan (SAP) will be prepared and finalized before database lock. The SAP will provide further details regarding the definition of analysis variables and analysis methodology to address all study objectives.

For the phase 2 Part 3 extension cohorts, the primary analysis of the primary endpoint will be performed when enrolled patients have had the opportunity to be assessed for response for at least 6 months after modakafusp alfa administration. Additional details of analyses will be provided in the SAP.

13.1.1 Analysis Sets

Full analysis set: The full analysis set will include all patients who receive at least 1 dose, even an incomplete dose, of modakafusp alfa, in the Part 3 extension cohorts. The full analysis set will be used for efficacy analysis.

Safety analysis set: The safety analysis set will include all enrolled patients who receive at least 1 dose, even an incomplete dose, of modakafusp alfa. The safety analysis set will be used for safety analysis.

Response-evaluable analysis set: The subset of the safety analysis set of patients treated at the MTD/OBD from the Part 2 dose expansion cohorts with measurable disease at baseline and at least 1 posttreatment efficacy evaluation. The response-evaluable analysis set will be used in the futility analysis of the Part 2 expansion.

PK analysis set: The PK analysis set will include those patients from the safety analysis set who have sufficient data to calculate at least 1 PK parameter for modakafusp alfa.

Immunogenicity-evaluable analysis set: Analysis will be based on available data from patients with a baseline assessment and at least 1 post-baseline immunogenicity assessment.

PRO analysis set: The PRO analysis set includes all patients with a baseline and at least one postbaseline measurement of any PRO. The analyses of PROs will be based on the PRO analysis set.

13.1.2 Analysis of Demographics and Other Baseline Characteristics

Patient demographic and baseline characteristics, including medical history, prior medications, and therapies, will be summarized using descriptive statistics. For continuous variables, descriptive statistics (number, mean, standard deviation, median, minimum, and maximum) will be provided. For categorical variables, patient counts and percentages will be provided. Categories for missing data will be presented if necessary.

13.1.3 Efficacy Analysis

Part 2

For the Part 2 expansion cohorts, the efficacy of modakafusp alfa will be evaluated by measuring the confirmed ORR defined as the proportion of patients who achieved a confirmed PR or better during study, duration of response, best overall response, CBR, DCR, TTP and PFS as defined by the IMWG Uniform Response Criteria (Appendix F). When appropriate, data from patients in the expansion cohorts will be summarized together with data from patients in the dose escalation phase.

For each cohort, the investigator-assessed best overall response and confirmed response (sCR, CR, VGPR, PR, MR, SD, or PD according to IMWG) for each patient who received at least 1 dose of study medication will be listed, and the exact 2-sided 95% CIs for the investigator-assessed confirmed ORR will be calculated based on the binomial distribution. Duration of response (in responders), PFS, and OS will be analyzed by using the Kaplan-Meier method. Descriptive statistics will be used to summarize the time to response in responders. All patients receiving at least 1 dose of modakafusp alfa will be considered evaluable for efficacy.

Part 3

The primary analysis for all efficacy endpoints in Part 3 extension cohorts will be based on the full analysis set. No formal statistical analysis will be performed to compare the 2 treatment arms.

The primary analysis of the primary endpoint ORR will be based on the responses assessed by the IRC. The number and percentage of patients with different response status will be presented. The ORR by IRC and the corresponding 95% exact CI will also be provided. Patients with unknown or missing response status will be treated as nonresponders, ie, these participants will be included in the denominator when calculating percentages of response.

Analysis of secondary endpoints will include the investigator-assessed ORR, DOR, CBR, duration of clinical benefit, DCR, duration of disease control, PFS, TTP, and OS as defined in Section 5.4.3. The investigator-assessed ORR, the IRC-assessed and investigator-assessed CBR and DCR will also be reported in the same approach as the primary endpoint. For all the time-to-event endpoints, the median time to event with 95% CI will be estimated by the Kaplan-Meier method. A Kaplan-Meier survival curve will be generated. The number and percentage of patients who had the event or were censored will also be reported.

Descriptive subgroup analyses of the primary endpoint by key baseline prognostic factors may be performed if data permit.

13.1.4 PK Analysis

PK parameters will be estimated using noncompartmental methods with Phoenix WinNonlin. The PK parameters will be estimated from the concentration-time profiles for the PK population. The following PK parameters will be determined in Parts 1 and 2, and in Chinese patients with the intensive PK schedule in Part 3, as permitted by data:

- C_{max}.
- t_{max}.
- AUC_∞.
- AUC_{last}.
- λ_z .
- $t_{1/2z}$.
- CL.
- V_{ss}.
- Accumulation ratio based on AUC_τ (area under the concentration-time curve during a dosing interval).

PK parameters will be summarized using descriptive statistics. Individual modakafusp alfa concentration-time data and individual PK parameters will be presented in listings and tabulated using summary statistics by dose cohort. Individual and mean concentration-time profiles will be plotted by dose cohort.

The PK data collected in this study are intended to contribute to future population PK analyses of modakafusp alfa. These population PK analyses may include data collected in other modakafusp alfa clinical studies. The analysis plan for the population PK analysis will be separately defined, and the results of these analyses will be reported separately.

13.1.5 Biomarker and Pharmacodynamic Analysis

During the clinical development of modakafusp alfa, several biomarkers will be assessed to test for their correlation with safety and, if possible, with efficacy. Markers that will be studied are markers linked either to the drug itself or to the treated disease. Markers of immune system activation (neopterin and others) will be summarized using descriptive statistics. Individual data will be listed. Summaries will be provided separately for each study phase and by dose, as applicable.

13.1.6 PRO Analyses

The PRO analysis will be based on the EORTC QLQ-MY20 subscale scores. The actual value and change from baseline of the EORTC QLQ-MY20 subscale scores will be summarized using descriptive statistics overall and by dose over time. The difference between baseline scores and scores over may be also explored using linear mixed models. EQ-5D-5L will be assessed using descriptive statistics over time.

The percentage of missing items for all questionnaires at each cycle will be described, as well as the number and percentages of patients with evaluable questionnaire (ie, questionnaire with at least 1 nonmissing item). PRO compliance and PRO completion over time will be calculated at the questionnaire level for the QLQ-MY20 at each cycle from baseline to provide context for the interpretation of PRO results. Rate of PRO score completion will be calculated as follows: (number of participants with the PRO score available at the visit) / (number of participants for

whom a PRO score is expected at the visit). Rate of available PRO scores over time will be calculated as follows: (number of participants with the PRO score available at the visit) / (total number of participants in the PRO analysis population). The PRO analysis population includes all patients with a baseline and at least 1 postbaseline measurement of any PRO.

13.1.7 Immunogenicity Analyses

The proportion of subjects with positive ADA (incidence, titer, and domain specificity) and NAb during the study will be summarized. The effect of immunogenicity on PK, pharmacodynamics, safety, and efficacy will be examined, if possible.

Analysis will be based on available data from patients with a baseline assessment and at least 1 post-baseline immunogenicity assessment (immunogenicity-evaluable analysis set). Summaries will be provided separately for each study phase and by dose, as applicable. All analyses will be descriptive and exploratory in nature.

13.1.8 Safety Analysis

The safety and tolerability of modakafusp alfa will be assessed by the recording of TEAEs (using NCI CTCAE, Version 5.0), vital signs, physical examination, chemistry, hematology, urinalysis, ECG, and concomitant medications.

TEAEs will be summarized using the safety analysis set and will be coded using the MedDRA. Data will be summarized using preferred terms and the primary SOC.

All patients receiving at least 1 dose of modakafusp alfa will be considered evaluable for the safety analysis. The AE incidence rates and the frequency of occurrence of overall toxicity, categorized by toxicity grades (severity), will be presented. Listings of laboratory test results and vital signs will be generated. Descriptive statistics summarizing the changes in laboratory tests over time will be reported.

13.2 Interim Analyses and Criteria for Early Termination

13.2.1 Part 2 Dose Expansion

A futility analysis will be conducted when 10 response-evaluable patients in a Part 2 arm have been followed for at least 3 cycles or have already responded or withdrawn. An arm with a posterior probability of success (PPOS) (ie, having 11 or more responders out of 25 patients) of <15% (ie, 3 or fewer responders in 10 patients) will stop enrollment for futility. Unless all 25 patients have already been enrolled, another futility analysis with the same decision rule based on PPOS will be conducted when 15 response-evaluable patients in a Part 2 arm have been followed for at least 3 cycles or have already responded or withdrawn. If there are 5 or fewer responders in 15 patients, enrollment will stop for futility.

13.2.2 Part 3 Extension

13.2.2.1 Part 3 Futility Stopping Rules

Two interim analyses for futility are planned for the Part 3 extension cohorts when approximately 15 and 48 patients of the planned 118 patients per arm are enrolled and treated for at least 3 cycles or have discontinued treatment prematurely. The futility stopping boundary will be determined based on the predictive probability of success at the primary analysis, using a Bayesian efficacy monitoring approach (Lee and Liu 2008). The treatment arm will be dropped for futility if the predictive probability of success at the primary analysis is found to be <10% based on the data from the interim analysis. Various prior distributions for the ORR are used for each treatment arm due to different prior efficacy information at different dose levels collected in Parts 1 and 2 of the study. To reflect the prior efficacy information for the 120 mg arm (40% ORR) collected in Parts 1 and 2, a weakly informative prior of Beta (1.2, 1.8) is used. However, because of comparatively limited efficacy data available at the 3 mg/kg (240 mg) dose, a noninformative prior of Beta (0.5, 0.5) is used. Based on these prior distributions, Table 13.a shows the stopping rules used for the treatment arms of 240 mg and 120 mg at each interim futility analysis. The details of the operating characteristics of the futility stopping rules are described in Appendix H.

There is no plan to stop for efficacy based on the interim analysis data.

Table 13.a Stopping Boundaries for 240 and 120 mg Arms at Each Interim Futility Analyses

	Number of patients enrolled and followed up	Recommend terminating the corresponding treatment arm due to lack of efficacy when number of responders is:			
for 3 month		240 mg Arm	120 mg Arm		
1st Interim Futility Analysis	15	≤2	≤1		
2 nd Interim Futility Analysis	48	≤10	≤10		

13.2.2.2 Part 3 Continuous Safety Monitoring Plan and Stopping Rules

In the Part 3 extension cohorts, an IDMC will review accumulating safety, tolerability, and efficacy data. Grade ≥4 nonhematologic treatment-related TEAEs, as well as treatment-related deaths, will be continuously monitored at the following time points using a Bayesian toxicity monitoring approach based on posterior probability (Table 13.b).

Table 13.b Safety Monitoring Time Points Based on Bayesian Stopping Rules

	Time Point
1st DMC Safety review	20 patients have been treated (10 patients in each arm).
2 nd DMC Safety review (first futility analysis)	15 patients in each arm treated for at least 3 cycles or discontinued treatment prematurely.
3 rd DMC Safety review (second futility analysis)	48 patients in each arm treated for at least 3 cycles or discontinued treatment prematurely.

DMC: Data Monitoring Committee.

The stopping rules will be determined based on the posterior probability of the unacceptable toxicity event rate >25%, and the unacceptable treatment-related death rate >5%. If there is at least an 80% probability that the true toxicity event (Grade ≥4 nonhematologic treatment-related TEAEs) rate is greater than 25% given the observed toxicity data, the enrollment will be paused until the IDMC reviews the data to avoid putting more patients at risk.

Similarly, if there is at least an 80% probability that the true treatment-related death rate is greater than 5% given the observed death data, the enrollment will be paused until the IDMC reviews the data. Details of the Bayesian toxicity monitoring plan and the operating characteristics can be found in Appendix I.

If the trial is stopped or paused for unacceptable toxicity or death, the regulatory agencies and investigators will be informed.

13.3 Determination of Sample Size

Part 1 of the study will follow a standard 3 + 3 dose escalation design. Under this design, the probability of dose escalation according to the true DLT rate is as follows:

True DLT rate	5%	10%	20%	30%	40%	50%	60%	70%
Probability of escalating	97%	91%	71%	49%	31%	17%	8%	3%

DLT: dose-limiting toxicity.

The probability of not observing a DLT in a sample size of 6 patients according to the true DLT rate is as follows:

True DLT rate	5%	10%	20%	30%	40%	50%	60%	70%
Probability of no toxicity	74%	53%	26%	12%	4.7%	1.6%	0.4%	<0.1%

DLT: dose-limiting toxicity.

Patients will be considered evaluable in Part 1 for MTD/OBD assessment provided they have not missed any of their infusions of modakafusp alfa in Cycle 1 and have not had a DLT. Patients who are not considered evaluable as defined above will be replaced.

Part 2 Expansion

The study will enroll up to 25 patients in each arm to further characterize safety of the OBD/MTD and obtain preliminary clinical efficacy data. An OBD/MTD dose will be considered clinically relevant if at least 11 out of 25 response evaluable patients have a confirmed PR or better. With a vague beta prior with shape parameters 0.428 and 1 for ORR (ie, mean of 30%), 11 responders out of 25 gives a greater than 90% posterior probability of true ORR being greater than 30%. The design has reasonable operating characteristics. With a true ORR of 30%, the probability of declaring success is 7%. In contrast, with a true ORR of 50%, the probability of declaring success is 70%.

Part 3 Extension

The primary objective of Part 3 of the study is to determine the confirmed ORR, including PR, VGPR, CR, and sCR assessed according to the IMWG criteria (Appendix F) to modakafusp alfa in patients with MM previously treated with ≥3 lines and with evidence of disease progression who are refractory to, or intolerant of, a PI, an IMiD, and an anti-CD38 mAb (triple refractory). The sample size was determined to claim that the true ORR is greater than the threshold response rate of 20% within each treatment arm. A total sample size of approximately 236 enrolled patients (118 patients per arm) will allow the study to have over 90% power to rule out an uninteresting response rate of 20% if the true rate is 35% with a 1-sided alpha of 0.025.

The purpose of the China continuation cohort is to allow continued evaluation of efficacy and any emerging safety signals in Chinese patients enrolled in China. After global patient enrollment is completed in Part 3, enrollment will continue for the China continuation cohort until about 15% of the total sample size is reached at the selected dose(s) (eg, 18 patients based on 118 patients treated at the selected dose[s]).

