7.13 Interim Analyses and Criteria for Early Termination

Part 2

A futility analysis will be conducted when 10 response-evaluable patients in a phase 2 arm have been followed for at least 3 cycles or have already responded or withdrawn. An arm with the predictive probability <15% (i.e., 3 or fewer responders in 10 patients) will stop enrollment for futility. Overall, avoidance of futility requires 11 or more responders out of the 25 patients to achieve 90% of the overall posterior probability of success (PPOS) at the final analysis. Unless all 25 patients have already been enrolled, another futility analysis with the same decision rule based on PPOS will be conducted when 15 response-evaluable patients in a phase 2 arm have been followed for at least 3 cycles or have already responded or withdrawn. If there are 5 or fewer responders in 15 patients, enrollment will stop for futility. However, the study team reserves the rights to continue the study if the patients still benefit from the study drug.

Part 3

In the Part 3 extension cohorts, an independent data monitoring committee (DMC) will review accumulating safety, tolerability, and efficacy data. The first DMC meeting will occur after approximately 20 patients (approximately 10 patients from each arm) have been enrolled and treated. The second and third DMC meeting will occur at the first and second interim futility analysis when approximately 30 and 96 patients (approximately 15 and 48 patients from each arm) have been enrolled and have completed 3 cycles of treatment or discontinue the treatment prematurely. The subsequent DMC meetings will be approximately every 6 months thereafter.

Futility Stopping Rules

Two interim analyses for futility are planned for the Part 3 extension cohorts when approximately 15 and 48 patients of the planned 118 patients per arm are enrolled and treated for at least 3 cycles or have discontinued treatment prematurely. The futility stopping boundary will be determined based on the predictive probability of success at the primary analysis, using a Bayesian efficacy monitoring approach. The treatment arm will be dropped for futility if the predictive probability of success at the primary analysis is found to be <10% based on the data

CONFIDENTIAL

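### Part 2's stated 7% false-positive rate is 7.6% (8% when rounded) with the futility stops followed, and could reach 9.8% if the SAP's continuation clause extends enrollment

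*Protocol*

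**What the plan says.** Protocol section 13.3 (Part 2 Expansion) calls a dose clinically relevant if "at least 11 out of 25 response evaluable patients have a confirmed PR or better". It then gives two operating characteristics: "With a true ORR of 30%, the probability of declaring success is 7" percent, and "In contrast, with a true ORR of 50%, the probability of declaring success is 70" percent. The synopsis (sample size justification) and SAP section 6.0 give the same pair.

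Protocol section 13.2.1 sets two futility looks, based on a 15% cut-off for the predictive probability of reaching 11 of 25. At 10 response-evaluable patients, an arm with a probability "of <15% (ie, 3 or fewer responders in 10 patients) will stop enrollment for futility". At 15: "If there are 5 or fewer responders in 15 patients, enrollment will stop for futility". The second look is conditional: "Unless all 25 patients have already been enrolled, another futility analysis with the same decision rule based on PPOS will be conducted".

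SAP section 7.13 gives the same boundaries and then adds: "However, the study team reserves the rights to continue the study if the patients still benefit from the study drug". The Protocol has no counterpart to that sentence. Neither document says whether the 7% and 70% assume that the futility stops are followed.

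**The concern.** The 7% and 70% are offered together as evidence that the design behaves reasonably, so they should come from one calculation under one set of assumptions. They do not appear to. In addition, the SAP contains a sentence that may loosen the futility stop, while still quoting figures that can only be approached if the stop is followed.

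At stake is the stated chance of calling a dose clinically relevant when its true ORR is only 30%. That rate applies separately to each of the four planned cohorts of 25. Protocol section 4.6.2 reports a 44% response rate in the 25-patient cohort at 1.5 mg/kg Q4W. Since 0.44 × 25 = 11, that result sits exactly on the threshold to which the error rate refers.

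**Working it through.** **Inputs.** Success: at least 11 of 25 (Protocol 13.3, SAP 6.0). Futility: stop at 3 or fewer of 10, and at 5 or fewer of 15 (Protocol 13.2.1, SAP 7.13). Prior: Beta(0.428, 1), mean 0.428/1.428 = 0.30 (Protocol 13.3). True rates p = 0.30 and 0.50.

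**Step 1: do the stated design elements agree with each other?**
- Posterior after 11 of 25 is Beta(11.428, 15), so P(ORR > 30%) = 92.0%. The plan states more than 90%.
- Predictive probability of reaching 11 of 25: 13.4% at 3/10 and 12.4% at 5/15, both below 15%; 39.0% at 4/10 and 37.0% at 6/15, both above.

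The threshold and both boundaries therefore follow from the stated prior. The operating characteristics can be computed exactly, without simulation.

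**Step 2: which assumption gives the stated 70%?** With both stops enforced,

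P(success | p) = Σ over x₁ ≥ 4 of b(x₁; 10, p) × Σ over x₂ with x₁ + x₂ ≥ 6 of b(x₂; 5, p) × P(Bin(10, p) ≥ 11 − x₁ − x₂),

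where b is the binomial probability. Without stops it is simply P(Bin(25, p) ≥ 11).

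At p = 0.50, the arm stops at the first look with probability 0.172 and at the second with probability 0.046, and succeeds with probability 0.698. Without stops the success probability is 0.788. The stated 70% therefore assumes that both stops are enforced.

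**Step 3: apply the same assumption at p = 0.30.** The arm stops at the first look with probability 0.650 and at the second with probability 0.123, so it reaches 25 patients with probability 1 − 0.650 − 0.123 = 0.227. It succeeds with probability 0.0758.

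| Futility handling | True ORR 30% | True ORR 50% |
|---|---|---|
| Stated in the plan | 7% | 70% |
| Both stops enforced | 7.58% | 69.8% |
| First look only (25 already enrolled by the second) | 8.04% | 71.4% |
| Every crossed boundary overridden, enrollment to 25 | 9.78% | 78.8% |

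**Step 4: is there another route to 7% with 70%?** Moving the second boundary to 6/15 gives 6.0% and 63.0%. Moving the first to 2/10 gives 8.4% and 74.0%. Ending at 24 patients with no stops gives 7.4% and 72.9%; ending at 24 with stops gives 6.1% and 66.2%. None of the variants tried gives both stated figures.

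**Step 5: size.** With stops enforced, the gap is 7.58 − 7 = 0.58 points. At the ceiling it is 9.78 − 7 = 2.78 points. Overriding every stop adds 9.78 − 7.58 = 2.20 points to the false-positive rate and 78.8 − 69.8 = 9.0 points to power.

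**The case against.** Four points can be made for the plan.

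First, 7.58% is only 0.08 points above the line at which a figure rounds to 7% rather than 8%. Truncation would print 7%. So would a modest simulation: if the figure was simulated with 10,000 runs (an assumption, since the documents do not say), the standard error is about 0.26 points and a correct program would print 7% more than a third of the time. This stands as an explanation of how the figure may have arisen. It does not make 7% the right value, because the exact one is easily computed.

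Second, a reader might infer that the SAP makes futility non-binding and that the false-positive rate therefore is 9.8%. The documents do not support that. The value 9.8% is reached only if every crossed boundary is overridden and enrollment runs to 25; any partial use falls between 7.6% and 9.8%. The SAP sentence can also be read as letting patients who benefit stay on treatment after enrollment has stopped, in which case the rate stays near 7.6%. The sentence follows directly on the enrollment stop and begins with a contrast, so reading it as an override is natural, but it is not the only reading.

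Third, the Protocol's own rule is to stop, so section 13.3 is not wrong for omitting a figure without stopping. This stands. The second pair of figures is needed only if the SAP clause permits further enrollment.

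Fourth, little depends on the figure. Part 2 is described as a preliminary evaluation, and section 4.6.2 bases Part 3 on all the Part 1 and Part 2 data, not on a controlled Part 2 error rate. This also stands and keeps the point minor.

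**Conclusion.** The stated 7% is not what the documented design delivers. On the assumption that reproduces the companion 70%, the figure is 7.6% and should read 8%; it is 8.0% if the second look does not take place. No documented reading gives 7% by ordinary rounding. The 9.8% is an upper bound that depends on what the SAP clause means. The point is minor: no boundary, threshold, sample size or Part 3 rule changes.

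The calculation assumes independent patients with a common true ORR, looks at exactly 10 and 15 response-evaluable patients, 25 response-evaluable patients at the end, no success declared in a stopped arm, and a response status at each look that equals the final status. Responses arising after a look would lower both enforced-stop probabilities, so they would not reconcile 7% with 70%.

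**What to change.** In the synopsis, Protocol section 13.3 and SAP section 6.0, restate the probabilities of declaring success as 8% at a true ORR of 30% and 70% at 50%, and say that they assume both futility stops are followed.

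Reconcile the last Part 2 sentence of SAP section 7.13 with Protocol section 13.2.1. If it permits enrollment to continue after a crossed boundary, also give the upper bounds of 10% and 79%, and put the provision in both documents. If it does not, say that it does not extend enrollment.

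The cost is about one sentence in each place and a slightly less favorable figure. No analysis, sample size or boundary needs to change.
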